Nurses experience burnout as a response to prolonged exposure to stressors (Hetherington et al., 2024). Burnout encompasses emotional exhaustion, depersonalization as a self-protective mechanism, withdrawal from communication when feeling inadequate, and a diminished sense of personal accomplishment (Zhang et al., 2020). A comprehensive meta-analysis reported that approximately three out of ten nurses experience burnout, highlighting the considerable prevalence of this issue (Li et al., 2024). The increasing prevalence of burnout in the nursing profession negatively impacts not only nurses' mental health but also their ability to communicate effectively (Cohen et al., 2023). Burnout substantially reduces nurses' capacity for therapeutic communication by impairing empathy and active listening skills (Mao et al., 2024; Yang et al., 2021). Hetherington et al. (2024) reported that burnout causes nurses to experience conflicting emotions and engage in increased avoidance behaviors. Additionally, higher communication competence among nurses has been found to be associated with lower levels of burnout (Lee et al., 2022). Challenges related to burnout and communication threaten not only nurses' mental well-being but also patient safety and the quality of care (Zhang et al., 2020). The COVID-19 pandemic has particularly highlighted the increased need for interventions aimed at improving nurses' well-being (Cohen et al., 2023). In this context, implementing programs that alleviate nurses' emotional burden and enhance their therapeutic communication skills is essential for promoting effective coping strategies and improving patient satisfaction (Li et al., 2024; Zhang et al., 2020). Various approaches, including Emotional Freedom Techniques (Dincer & Inangil, 2021), Mindfulness-Based Stress Reduction training (Talebiazar et al., 2025), and the Communicating Oncologic Prognosis with Empathy Guide (Lippe et al., 2020), have shown positive outcomes. However, despite these results, burnout and patient-nurse relationship problems continue to increase among nurses (Cohen et al., 2023). A meta-analysis has highlighted that health policies should prioritize protecting healthcare workers, in addition to improving working conditions (Quesada-Puga et al., 2024). In this context, Balint therapy has been proposed as a novel and effective counseling approach to support nurses.

In Balint groups, nurses explore strategies to better manage challenging patient-nurse relationships and enhance their interpersonal skills (Huang et al., 2020). These groups are particularly effective in raising awareness of the emotions and thoughts associated with patients perceived as "difficult" (Yousefzadeh et al., 2024). Balint-based interventions also provide social support by creating a relatively safe environment while respecting nurses' professional experiences (Lv, 2023). Moreover, considering nurses' working conditions, Balint-based interventions are regarded as easily implementable, time-efficient, and evidence-based approaches (Yang et al., 2021).

Rationale

Previous studies have primarily examined the effectiveness of Balint therapy among residents and medical students (Huang et al., 2020a; McCarron et al., 2024). In recent years, there has been growing interest in implementing Balint groups with nurses (Lu et al., 2020). Existing literature indicates that Balint therapy is effective in reducing burnout and enhancing self-efficacy (Shan et al., 2024), improving communication skills (Yang et al., 2021), and promoting quality of work-life among nurses (Huang et al., 2020). However, further research is needed to examine the long-term effects and sustainability of this intervention among nurses. To the best of our knowledge, this study represents the first application of a Balint-based intervention with nurses in the country, highlighting a gap in the literature regarding its effectiveness. Given the demanding working conditions of nurses, a Balint-based group intervention may provide meaningful support for their psychosocial well-being and facilitate positive patient care outcomes.

The current study aims to measure the effect of a Balint-based group intervention on burnout and communication skills in nurses. The research hypotheses are as follows:

H0-1: There is no significant difference in burnout levels between the intervention and control groups.

H0-2: There is no significant difference in communication skills between the intervention and control groups.

Study design

The study used a two-arm parallel-group randomized controlled design with pre-test and post-test measurements and follow-up assessments at one and three months.

Methods

Participants were nurses recruited through purposive sampling in 2025. A power analysis was conducted to determine the required sample size for the intervention and control groups. Based on a previous study examining the effect of Balint group training on burnout (Huang et al., 2020), the minimum required sample size was calculated as 28 participants, with an alpha (α) level of 0.05, an effect size (d) of 1.70, and a power of 99%. Considering the nurses' shift schedules, potential attrition was anticipated.

All nurses working in hospitals across various cities nationwide where the study was conducted were invited to participate through announcements posted on social media platforms. The inclusion criteria were: (i) having worked as a nurse in the same clinical setting for at least one year and (ii) providing informed consent to participate. The exclusion criterion was the presence of a communication impairment that could hinder participation (e.g., hearing or speech disorder). The criteria for discontinuation from the study included: (1) voluntary withdrawal, (2) missing at least two sessions, and (3) incomplete or missing data on the study instruments.

A total of 50 nurses contacted the research team and underwent eligibility screening. Of these, 17 declined participation after learning that session attendance was mandatory, and three did

not meet the inclusion criteria. Ultimately, 30 nurses who met the inclusion criteria were enrolled in the study, taking anticipated attrition into account.

Randomization and prevention of bias

Participants were randomly assigned to either the intervention or control group at a 1:1 ratio using simple randomization. An independent academic not involved in the study generated a random number list via a computer program to minimize selection bias. Eligible nurses were then sequentially allocated to the intervention ($n = 15$) and control ($n = 15$) groups according to the random sequence. Group assignments were determined using a lottery method conducted by two independent academics unaffiliated with the study. The letter “X” represented the intervention group, while “Y” represented the control group. Due to the nature of the Balint group intervention, blinding of participants and researchers was not feasible. Nevertheless, allocation concealment was maintained: data were coded (Group X/Group Y) and analyzed by an independent statistician blinded to group assignments to minimize bias.

Procedure

This study will be conducted on an online platform from December 2024 to May 2025. Participating nurses received an online information form and a voluntary consent form. After reviewing the information, participants provided electronic consent. Only those who consented were included in the online intervention sessions.

Intervention group sessions were held once a week, each lasting 45–50 minutes, without disrupting nurses’ rest periods or shift schedules. The intervention group was organized as a closed group. Session days were scheduled according to nurses’ weekly work schedule. The groups were facilitated by two academically qualified researchers specializing in psychiatric nursing, each trained in psychotherapy techniques, including psychodrama and cognitive behavioral therapy. Sessions were conducted online in a quiet environment, with the screen layout designed to allow participants to see one another clearly. Nurses participated in Balint-based group counseling for six weeks. Post-tests were administered immediately after the final session (Session 6). The first follow-up assessment was conducted one month after the intervention, and the second follow-up assessment took place three months post-intervention.

Intervention

The intervention in this study consisted of nurse-led group counseling based on the Balint approach. The primary objectives of a Balint group are to deepen understanding of the nurse–patient relationship, enhance nurses’ awareness of their own emotions, thoughts, and behaviors within that relationship, and provide a supportive environment for participants (Huang et al., 2020). In this study, weekly sessions followed a structured format adapted from the recommendations of the International Balint Federation (https://www.americanbalintsociety.org/reference_library.php). The first session included an additional 30 minutes to explain the study’s purpose and procedures, establish a confidentiality agreement, and clarify group rules and expectations (e.g., maintaining confidentiality, being respectful and non-judgmental, ensuring all members have an opportunity to speak, and

attending sessions punctually). This preparation ensured that participants were fully prepared to engage in the intervention.

Phase 1 (Case Presentation): In each session, a different group member (the case presenter) shared a case involving a patient interaction that elicited intense or challenging emotions (e.g., distress, helplessness, frustration, anger). The case presenter elaborated on their feelings, thoughts, and behaviors regarding the situation, providing details about when, where, and how it occurred.

Phase 2 (Exploration): Group members asked questions to better understand the dynamics of the nurse–patient relationship in the case, while avoiding direct advice or criticism. The case presenter clarified ambiguous points and had the opportunity to explore their own experiences more deeply.

Phase 3 (Group Discussion): The group leader asked the case presenter to temporarily withdraw and remain silent during the discussion. Group members then discussed various aspects of the nurse–patient relationship, sharing their own feelings and perspectives. The group leader encouraged members to explore their emotions in depth and guided the discussion toward the dynamics of the nurse–patient relationship. By preventing criticism directed at the case presenter, the leader ensured a safe environment and effectively managed session time.

Phase 4 (Feedback): After the discussion, the case presenter rejoined the group to share new perspectives and emotional insights gained from the discussion. Group members then provided general evaluations of the process and highlighted their learning points.

Phase 5 (Closing): The group leader summarized the prominent themes that emerged during the session, offered a brief evaluation, and concluded the session in a structured manner.

Control group

Nurses in the control group continued their routine work schedules and did not receive any additional training or psychosocial support during the study period. Data collection instruments were administered to the control group concurrently with the intervention group. Because the nurses in the control group were employed at different hospitals and were unfamiliar with one another, the risk of information sharing between groups was minimized. After the study was completed, the control group was informed about the intervention; however, no additional counseling services were provided due to scheduling constraints related to their working hours.

Outcome measures

The Participant Information Form was prepared by the researchers based on literature (Huang et al., 2020; Elzain et al., 2023). This form consists of seven questions to determine participants age, gender, educational status, marital status, physical and mental health status, years of employment.

Primary Outcome Measure: The Maslach Burnout Inventory (MBI) was developed by Maslach and Jackson (1981), and its Turkish validity and reliability were established by Ergin (1992). The MBI is a self-report instrument used to assess burnout levels and consists of 22 items across

three subscales: Emotional Exhaustion, Depersonalization, and Personal Accomplishment. Each item is rated on a 0–4 scale. Higher scores on the Emotional Exhaustion and Depersonalization subscales indicate greater burnout, whereas higher scores on the Personal Accomplishment subscale indicate lower burnout. In this study, the Personal Accomplishment subscale was reverse-coded so that all subscales aligned in the same direction, with higher total scores reflecting higher levels of burnout. Ergin (1992) reported Cronbach's alpha (α) coefficients for the Emotional Exhaustion, Depersonalization, and Personal Accomplishment subscales as .83, .65, and .72, respectively. In the present study, Cronbach's alpha coefficients for the pre-test, post-test, first follow-up, and second follow-up assessments were .85, .89, .87, and .88, respectively.

Secondary Outcome Measures: The Communication Skills Scale for Health Professionals (CSSHP) was developed by Leal-Costa et al. (2016), and its Turkish validity and reliability were established by Mendi et al. (2020). The scale is a self-report instrument designed to assess the communication skills of health professionals. It comprises 18 items across four subscales, with each item rated on a 1–6 Likert scale. Higher scores indicate better communication skills. Mendi et al. (2020) reported Cronbach's alpha (α) values for the subscales ranging from .72 to .79. In the present study, Cronbach's alpha coefficients for the pre-test, post-test, first follow-up, and second follow-up assessments were .89, .88, .92, and .92, respectively.

Statistical analysis

Data analysis was conducted using IBM SPSS Statistics for Windows, version 26.0 (IBM Corp., Armonk, NY, USA). The dataset was screened for missing values and assessed for normality assumptions prior to analysis. Differences between the intervention and control groups were examined using Pearson's chi-square test for categorical variables and the independent samples t-test for continuous variables. Fisher's exact test was applied when the expected cell count was less than five. A two-way mixed ANOVA was performed to evaluate between-group, within-time, and group \times time interaction effects. Bonferroni correction was applied for multiple comparisons. Effect sizes were reported using Cohen's d for within-group comparisons and partial eta squared (η^2) for the mixed ANOVA. The interpretation of partial eta squared values followed the classifications proposed by Cohen (1992): $\eta^2 \geq .01$ was considered small, $\eta^2 \geq .06$ moderate, and $\eta^2 \geq .14$ large. Statistical significance was set at $p < .05$.

Ethical considerations

Ethical approval for this study was obtained from the Bilecik Seyh Edebali University Non-Interventional Clinical Research Ethics Committee (19.09.2024 – 280361). Prior to participation, nurses were provided with detailed information about the purpose of the study, the procedures to be performed, and the voluntary nature of participation. Informed consent was obtained electronically from all participants via an online consent form. Participants were assured of confidentiality, the right to withdraw from the study at any time, and that their personal information would not be shared.

References

Cohen, J. (1992). Statistical power analysis. *Current Directions in Psychological Science*, 1(3), 98–101. <https://doi.org/10.1111/1467-8721.ep10768783>

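### The attendance rule can remove only intervention nurses after randomisation, and no analysis set keeps them in the comparison

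*Combined protocol and SAP*

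**What the plan says.** The participant paragraphs of the Methods set the rule: "The criteria for discontinuation from the study included: (1) voluntary withdrawal, (2) missing at least two sessions, and (3) incomplete or missing data". Under Procedure, "Intervention group sessions were held once a week" and "Nurses participated in Balint-based group counseling for six weeks". Under Control group, "Nurses in the control group continued their routine work schedules and did not receive any additional training or psychosocial support"; these nurses only complete the instruments, at the same times as the intervention arm.

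The Statistical analysis section states "The dataset was screened for missing values and assessed for normality assumptions prior to analysis", and then "A two-way mixed ANOVA was performed to evaluate between-group, within-time, and group" by time effects. It names no intention-to-treat, full or per-protocol set, no method for missing data and no sensitivity analysis. It does not say which of the three ANOVA effects is decisive. The first hypothesis, in the Rationale, is worded as a comparison of levels: "There is no significant difference in burnout levels between the intervention and control groups".

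**The concern.** A control nurse has no sessions to miss, so the second criterion acts after randomisation and on one arm only. The other two criteria can remove nurses from either arm and have no built-in direction.

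The document does not state that discontinued nurses are left out of the analysis. That reading follows from three features: the rule ends participation in the study rather than in the sessions; incomplete data stands in the same list; and the planned ANOVA, in its usual form, discards anyone without all four scores. Nothing elsewhere brings these nurses back.

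A link between absence and burnout is plausible on the document's own account, since its introduction associates burnout with avoidance. If the more burnt-out nurses stop attending and are dropped, the intervention arm's mean burnout falls without any treatment effect. A comparison of levels, which is how the first hypothesis is worded, is the most exposed.

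**Working it through.** **The plan's own figure.** With d = 1.70, two-sided alpha 0.05 and a two-sample t-test (noncentral t), 14 per arm gives power 0.991. The stated minimum of 28 at 99% power is reproduced. Power is 0.994 with 15 v 15 and still 0.984 with 11 v 15, so loss of power is not the issue.

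**How many nurses might be removed.** The document gives no absence rate, so assume each of six sessions is missed independently with probability p. Then q = P(at least 2 missed) = 1 − (1−p)^6 − 6p(1−p)^5. The expected number removed is 15q, and the chance of at least one removal is 1 − (1−q)^15.

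| p | q | expected removals of 15 | chance of at least one |
|---|---|---|---|
| 5% | 3.3% | 0.5 | 39% |
| 10% | 11.4% | 1.7 | 84% |
| 15% | 22.4% | 3.4 | 98% |

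**Size of the bias with no true effect.** Drop the k nurses of 15 who rank highest on a non-attendance score that has correlation r with the final burnout score. The remaining mean falls by r × S_k / (15 − k) SD, where S_k is the sum of the k largest expected normal order statistics for n = 15 (1.736, 1.248, 0.948, 0.715).

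- k = 2, r = 0.5: 0.5 × 2.984 / 13 = 0.11 SD.
- k = 4, r = 0.5: 0.5 × 4.647 / 11 = 0.21 SD.
- If absence instead tracks the nurse's stable burnout level, with within-person correlation 0.6 (assumed), multiply by √0.6 = 0.775. This gives 0.09 and 0.16 SD.

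**Error rates.** These come from simulation: 40,000 runs per case, 15 v 15, four assessments, within-person correlation 0.6, r = 0.5 and 2 to 4 intervention nurses removed. Ranges cover both forms of selection unless one is named.

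| Comparison | bias favouring intervention | false positives |
|---|---|---|
| Final score | 0.09–0.21 SD | one-sided 4.2–7.9% (nominal 2.5%); two-sided about 5.8–8.4% (nominal 5%) |
| Between-group main effect | 0.08–0.16 SD | one-sided 4.5–7.2% |
| Change from pre-test to 3 months, selection on stable level | about 0 | one-sided 2.4–2.5% |
| Change from pre-test to 3 months, selection on final score | 0.05–0.09 SD | one-sided 3.5–4.1% |
| Group-by-time F test | – | 5.0–5.5% (nominal 5%) |

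**Other assumptions, final score.** At r = 0.3 with 2 to 4 removed, the bias is 0.05–0.13 SD. With one nurse removed at r = 0.5 it is 0.05–0.06 SD. At r = 0 it is zero. At r = −0.5 it is 0.09–0.21 SD against the intervention.

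**Complete-case loss in both arms.** If a fraction m of forms is missing at each of the three post-baseline assessments, the complete-case ANOVA keeps 30 × (1 − m)^3 nurses: 28.2 at m = 2% and 25.7 at m = 5%.

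**The case against.** The strongest reply is that the exclusion is inferred and may have had no effect. The text never says that discontinued nurses were left out. The flow diagram could not be seen here and may show the numbers analysed by arm. Seventeen nurses declined before randomisation because attendance was compulsory, so the 30 enrolled had accepted that condition, and sessions were fitted around shifts. Under the binomial model above, two or more removals have only an 8.5% chance at 5% absence and 52% at 10%. The two-sided error is inflated only modestly, and the largest bias shown is 0.21 / 1.70 = 12% of the planning effect. The interaction, often the test of interest in a pre-test/post-test design, is nearly untouched. A stand-alone final-score test is not explicitly named as an outcome analysis.

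Much of this stands as context. It limits the likely size, and absent counts cannot be held against the plan while the diagram is unseen. It does not make the rule two-sided or supply an analysis set. The plan also tests the between-group effect without ranking it below the interaction, and d = 1.70 is a planning value from an earlier study, not a result of this trial.

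One further point is right. If data collection stopped when a nurse was discontinued, a refitted model relies on a missing-at-random assumption and cannot fully recover the as-randomised comparison.

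**Conclusion.** The concern holds. That the attendance rule acts on one arm only follows from the design and needs no assumption. That it leads to exclusion from the analysis is the natural reading of a plan with no defined analysis set and a complete-case method.

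The size depends on two quantities that the document does not give: how many nurses were removed, and how absence relates to burnout. Under the moderate assumptions used here, the bias in a comparison of levels is roughly 0.1 to 0.2 SD. It is smaller with a single removal and nil with none. The direction is conditional too. This should be fixed, but it does not by itself overturn the trial.

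**What to change.** - State the primary analysis set: all 30 randomised nurses, in the arm allocated, whatever their attendance. Neither attendance nor an incomplete form should be a reason for removal from the analysis.
- Replace the complete-case mixed ANOVA with a likelihood-based linear mixed model, or multiple imputation, that uses every available assessment.
- Report removals and missing forms by arm and reason, including zero if there were none.
- Present the analysis of nurses who missed fewer than two sessions only as a labelled per-protocol sensitivity analysis.
- If scores were not collected after discontinuation, say so and state the missing-at-random assumption openly.

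The Outcome measures section already reports reliability at the last assessment ("alpha coefficients for the pre-test, post-test, first follow-up, and second follow-up assessments were .85, .89, .87, and .88"), so this is mainly a change to analysis and reporting. If any assessments are still to come, collect them regardless of attendance; the outcomes are self-report and the study runs online.

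The cost is a few sentences in the SAP, one refitted model and a short table, with no new data if collection is complete. The downside is slightly more analysis work and an estimate that may be smaller than the effect among attenders.

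### Incomplete questionnaire data is a reason to leave the study, with no limit by scale, visit or amount, so a gap in the secondary scale can remove a nurse from the primary burnout comparison

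*Combined protocol and SAP*

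**What the plan says.** The participants text under Methods introduces three criteria with the words "The criteria for discontinuation from the study included". They are voluntary withdrawal, absence from two or more sessions, and "3) incomplete or missing data on the study instruments". The third has no threshold, names no visit and covers the instruments together.

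Under Outcome measures, the MBI is primary: "The MBI is a self-report instrument used to assess burnout levels and consists of 22 items across" three subscales. The CSSHP is secondary: "It comprises 18 items across four subscales, with each item rated on a 1–6 Likert scale". Both have reliability coefficients reported for pre-test, post-test and the two follow-ups, so each was given four times.

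On missing data, Statistical analysis says only this: "The dataset was screened for missing values and assessed for normality assumptions prior to analysis". The main analysis is a two-way mixed ANOVA. The documents give no scoring rule for part-complete forms, no imputation, no analysis set, no intention-to-treat statement, and no rule that keeps data collected before a nurse is discontinued.

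**The concern.** The wording ties membership of the primary dataset to behaviour on another outcome. A nurse with four complete MBI forms meets the criterion if her CSSHP is incomplete at three months. A nurse with a gap at post-test meets it before her follow-up forms are due.

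An exclusion decided after randomisation does harm when it is related to the outcome or differs between arms. Both are plausible here. The background section itself associates burnout with avoidance behaviour, although it does not mention questionnaires. Intervention nurses meet weekly and take the post-test straight after the last session, while control nurses receive no support during the study and no counselling afterwards, so equal response cannot be assumed. Because no threshold is set, applying the criterion also takes judgement. The plan states that researchers were not blinded and does not say who applies it.

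With 15 nurses per arm, few exclusions are needed to move a mean. As an illustration on assumed values, removing 2 of 15 nurses who average 1 SD above their arm mean lowers that mean by 2/13 = 0.15 SD.

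**Working it through.** **The plan's sample size.** The inputs from Methods are "alpha (α) level of 0.05", "an effect size (d) of 1.70", power 99% and 1:1 allocation. Sidedness is not stated, so I take it as two-sided. A two-sample t-test with the noncentral t distribution gives 99.1% power at 14 per arm and 98.6% at 13 per arm, so the stated minimum of 28 reproduces. Enrolment of 30 leaves room for 30 − 28 = 2 losses (2/30 = 6.7%).

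**Power after losses, at d = 1.70.** Power is 99.4% at N = 30, 98.6% at N = 26 and 94.9% at N = 20. Power is therefore not the main harm.

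**Items exposed to the criterion.** Each assessment has 22 + 18 = 40 scale items. Four assessments give 160, of which 88 are MBI and 72 (45%) are CSSHP. The seven-question information form is left out. If pre-test came before randomisation, which the documents do not say, only three assessments can cause a post-randomisation exclusion. That is 120 items, of which 66 are MBI.

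**Nurses meeting the criterion under its literal reading.** With independent blanks at rate r per item, P = 1 − (1 − r)^k over k items. The documents give no r, so a range is shown for four assessments.

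| r (assumed) | Both scales, k = 160 | MBI only, k = 88 |
|---|---|---|
| 0.05% | 7.7% | 4.3% |
| 0.1% | 14.8% | 8.4% |
| 0.2% | 27.4% | 16.2% |
| 0.5% | 55.2% | 35.7% |

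At r = 0.1% these are 30 × 0.148 = 4.4 nurses and 30 × 0.084 = 2.5 nurses. The share who meet the criterion through the CSSHP alone is 14.8 − 8.4 = 6.4%, or about 1.9 nurses of 30.

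For the three assessments after pre-test at the same rate, both scales give 1 − 0.999^120 = 11.3% and MBI items alone give 1 − 0.999^66 = 6.4%. The CSSHP-only share is then 11.3 − 6.4 = 4.9%, about 1.5 nurses.

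**Whole forms missed instead of items.** At an assumed 2% per form, eight independent forms give 1 − 0.98^8 = 14.9% and the four MBI forms alone give 1 − 0.98^4 = 7.8%. If a nurse who misses a visit misses both scales, there are only four independent events. The figure is then 7.8% with or without the CSSHP, and the excess is zero.

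**The case against.** The strongest reply is that the text says less than a reader might infer. It does not speak of a single blank item, of either scale or of any visit; that breadth comes only from the absence of limits. The criterion could have been meant for forms never returned. A reader might go further and infer that completed MBI data were deleted, or that later questionnaires were withheld. No section says either. Reliability coefficients at all four assessments show that collection continued for at least some nurses. This stands, and the point rests on what the criterion permits.

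Much of the loss would also occur without the criterion. A standard mixed ANOVA needs complete repeated measures, so a nurse without an MBI score at one visit drops out of it anyway. In the present analysis the criterion adds mainly the CSSHP-only share. This also stands, and it means that deleting the criterion without changing the model would recover only part of the data.

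That share depends in turn on independence. Blanks clustered within nurses would affect fewer of them. The study ran online, and if answers were forced and nurses miss both scales together, the excess is near zero. The documents do not say whether answers were forced.

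Finally, the number removed may be zero. The flow diagram, where losses would normally appear, is not in the text available, and nothing in the documents shows that nurses who skip items are the more exhausted ones. The size and direction of any bias are therefore unknown. This limits the claim but does not make the criterion harmless: it remains a stated rule that excludes randomised nurses on post-randomisation behaviour, and nothing elsewhere contains it.

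**Conclusion.** The point holds in a limited form. The third discontinuation criterion lets an incomplete secondary scale, or a gap at one visit, remove a nurse from the primary comparison, and no rule retains her data. The consequence is possible bias in the burnout comparison in either direction. Loss of power is minor if d = 1.70 is right (98.6% at N = 26).

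The extent cannot be determined from the documents. On an assumed independent blank rate of 0.1% per item, 14.8% of nurses meet the criterion over four assessments, or 11.3% over the three after pre-test if that preceded randomisation. The corresponding MBI-only figures are 8.4% and 6.4%. The excess due to the CSSHP ranges from these differences down to about zero under forced answers and visit-level non-response. None of these figures estimates what happened in the trial, and a reader should not conclude that about 15% of nurses were lost. The change should be made because it is cheap and removes an avoidable source of bias.

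**What to change.** 1. Delete incomplete or missing questionnaire data as a reason for discontinuation, and keep every randomised nurse in her assigned arm.
2. Handle missing data separately for each instrument and visit. A CSSHP gap never removes MBI data, and a gap at one visit does not end later collection.
3. Score part-complete forms by one rule, fixed before unblinding and applied to both arms. The documents give no basis for a particular threshold, so the plan should state one with its source and say how it carries through to the MBI total.
4. Analyse all available MBI scores with a likelihood-based mixed model (group, time, group × time) in place of the complete-case mixed ANOVA. Without this step, nurses missing an MBI visit are still dropped.
5. Since data appear already to have been collected, restore the available data of any nurse removed under this criterion. Report incomplete forms and exclusions by arm, instrument and visit. Forms never collected cannot be recovered.

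The cost is wording in the participants and analysis sections, a few lines of scoring code and a refitted model. The downside is that a few scores rest on within-scale imputation, and that the model assumes data are missing at random.
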